12.9.13. Non-ICH Listings

Non-ICH: Listings					
No.	Population	IDSL / Example Shell	Title	Programming Notes	Deliverable [Priority]
PK concentration and derived PK parameters					
28.	PK	PKCL1	Listing of GSK2330811 Plasma Concentration-Time Data	Add data dependent footnote: 'Note: NA=Not Available [data dependent], NQ=Non-Quantifiable, LLQ value=100ng/mL'	SAC
29.	PK	PKCL1	Listing of Derived GSK2330811 Pharmacokinetic Parameters		SAC
Serum levels of OSM					
30.	PK	PKCL1	Listing of Serum Level of OSM	Include both Free and Total OSM Add footnote: 'Note: BLQ = Below the limit of quantification which is 2.5pg/ml for both free and total OSM'	SAC
31.	Safety	PKCL1	Listing of Derived Total OSM Pharmacokinetic Parameters		SAC
Serum levels of TPO and EPO					
32.	PK	PKCL1	Listing of Level of Thrombopoietin in Serum		SAC
33.	PK	PKCL1	Listing of level of Erythropoietin in Plasma		SAC
Other					
34.	Enrolled	PAN12	Listing of COVID-19 Assessments and Symptom Assessments for Subjects with COVID-19 Adverse Events		SAC
35.	Enrolled	PAN7	Listing of All Subjects with Visits and Assessments Impacted by COVID-19 Pandemic		SAC

CONFIDENTIAL

208564

12.10. Appendix 10: Example Mock Shells for Data Displays

Example: SAFE T1

Protocol: 208564

Population: Safety

Page 1 of n

Table XX.XX
Summary of Chemistry Results by Maximum CTCAE Grade

Test: Creatinine (UMOL/L)

Event: Creatinine increased

Treatment	N	Grade 1	Grade 2	Grade 3	Grade 4
Placebo	XX	XX	XX.X	XX.XX	XX.X
GSK2330811 450 mg	XX	XX	XX.X	XX.XX	XX.X

Note: CTCAE criteria, V5.0: November 17, 2017 graded on laboratory test value.

Only events with at least one graded value are shown.

CONFIDENTIAL

208564

Example: SAFE_T2

Protocol: 208564

Population: Safety

Page 1 of n

Table XX.XX

Summary of Nadirs for Selected Haematology Parameters [as Percent Change from Baseline]

Lab Test (unit)	Treatment	N	n	Mean	SD	Median	Min	Max
Hemoglobin (G/L)	Placebo	XX	XX	XX.X	XX.XX	XX.X	XX.X	XX.X
	GSK2330811 450 mg	XX	XX	XX.X	XX.XX	XX.X	XX.X	XX.X

.....

Note: Nadir is the lowest post-baseline value of the parameter.

CONFIDENTIAL

208564

Example: SAFE_T3

Protocol: 208564

Population: Safety

Page 1 of n

Table XX.XX
Summary of Days to Nadir for Selected Haematology Parameters

Lab Test (unit)	Treatment	N	n	Median	Min	Max	Range
Hemoglobin (G/L)	Placebo	XX	XX	XX	XX	XX	XX
	GSK2330811 450 mg	XX	XX	XX	XX	XX	XX

.....

Note: Nadir is the lowest post-baseline value of the parameter.

CONFIDENTIAL

208564

Example: SAFE_T4

Programming note: please flag to study team/ statistics when summarizing if observe any character variables not the minimum value and not presented as an increase category.

Tests to summarise as X=BACTM_URQ (minimum value=NONE SEEN)

Tests to summarise as Y= BLD_URC, PROT_URG, KETO_URG, GLUC_URG (minimum value=NEGATIVE)

Tests to summarise as Z= RBCM_URG, WBCM_URG (minimum value=NONE SEEN)

Tests to summarise as W= SG_URG (minimum value=Low)

Example modified from UR1

Protocol: ABC123456

Page 1 of 1

Population: Safety/Other study specific

Table X
Summary of Worst Case Urinalysis Results Post-Baseline Relative to Baseline

Test	n	Treatment A (N=248)		Treatment B (N=247)	
X		230		232	
	No Change/Decreased	222 (97%)		223 (96%)	
	Any Increase	8 (3%)		9 (4%)	
	Increase to MANY	6 (3%)		5 (2%)	
Y	n	230		232	
	No Change/Decreased	222 (96%)		222 (96%)	
	Any Increase	7 (3%)		10 (4%)	
	Increase to TRACE	2 (<1%)		5 (2%)	
	Increase to 1+	1 (<1%)		4 (2%)	
	Increase to 2+	1 (<1%)		0	
	Increase to 3+	4 (2%)		1 (<1%)	
Z	n	230		232	
	No Change/Decreased	222 (96%)		222 (96%)	
	Any Increase	7 (3%)		10 (4%)	
	Increase to 0-1	2 (<1%)		5 (2%)	
	Increase to 5-10	1 (<1%)		4 (2%)	
	Increase to 10-15	1 (<1%)		0	
	Increase to 15-20	2 (<1%)		1 (<1%)	

CONFIDENTIAL

208564

	Increase to 20-25	2 (<1%)	0
	Increase to 25-50	4 (2%)	1 (<1%)
W	n	230	232
	No Change/Decreased	222 (97%)	223 (96%)
	Any Increase	8 (3%)	9 (4%)
	Increase to NORMAL	6 (3%)	5 (2%)
	Increase to HIGH	6 (3%)	5 (2%)

Note: Little n does not include Not done or No results.

CONFIDENTIAL

208564

Example: SAFE_T5

Protocol: 208564

Population: Safety

Page 1 of n

Table 3.22
 Summary of Worst Case Vital Sign Results Relative to Change from Baseline Potential Clinical Importance (PCI) Criteria

Test (Unit)	Change Category	Placebo (N=XX)	GSK2330811 450 mg (N=XX)
Diastolic blood pressure (mmHg)	n	xx	xx
	Decrease >= 10	xx (xx%)	xx (xx%)
	Decrease >= 20	xx (xx%)	xx (xx%)
	Increase >= 10	xx (xx%)	xx (xx%)
	Increase >= 20	xx (xx%)	xx (xx%)
Heart Rate (bmp)	n	xx	xx
	Decrease >= 15	xx (xx%)	xx (xx%)
	Decrease >= 30	xx (xx%)	xx (xx%)
	Increase >= 15	xx (xx%)	xx (xx%)
	Increase >= 30	xx (xx%)	xx (xx%)
Systolic blood pressure (mmHg)	n	xx	xx
	Decrease >= 20	xx (xx%)	xx (xx%)
	Decrease >= 40	xx (xx%)	xx (xx%)
	Increase >= 20	xx (xx%)	xx (xx%)
	Increase >= 40	xx (xx%)	xx (xx%)

[figure not shown]
CONFIDENTIAL

208564

Example: SAFE_F1
 Protocol: 208564
 Population: Safety

Page 1 of n

Figure XX.XX
 Participant Profiles for Haematology by Treatment Group

Programming notes:

One legend including all participants.

Make plot as large as possible to fill space.

add (P) to denote placebo participants.

y-axis will be displayed on the left-hand side plot and the labels for the reference lines will be included on the right-hand side plot.

[figure not shown]
CONFIDENTIAL

208564

Example: SAFE_F2
 Protocol: 208564
 Population: Safety

Page 1 of n

Figure XX.XX
 Mean Profile for Haematology by Treatment Group

Programming notes:

See output 3.9 from 201247.

Make plot as large as possible to fill space.

Use different marker symbol, line pattern and colour by treatment group.

Table: Include N after treatment group and use same colour as in the plot.

[figure not shown]
CONFIDENTIAL

208564

Example: SAFE_F3
 Protocol: 208564
 Population: Safety

Page 1 of n

Figure XX.XX
 LTF Patient Profiles

Note: M = Male, F = Female, ALT = Alanine Amino Transferase, AST = Aspartate Amino Transferase, Alk. Phos. = Alkaline Phosphatase, Total Bili. = Total Bilirubin
 Clinical Concern Levels: ALT, AST and Alk. Phos: 2 times respective ULN, Total Bili: 1.5 times the ULN

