9.4.2. Primary Endpoint(s)

Analysis	Details
Endpoints	
 • Number of participants reporting AEs and SAEs • Number of participants with vital signs (blood pressure, heart rate, body temperature) reaching a threshold of potential clinical importance • Number of participants with treatment emergent abnormal ECG findings. • Number of participants with CTCAE grade 1 or higher safety laboratory results (clinical chemistry, haematology values where CTCAE grading applies). • Number of participants with treatment emergent abnormal urinalysis findings.
Analysis	
 • For count data, the number and percentage of participants will be presented. • In addition, where continuous data is available, descriptive statistics (i.e. n, arithmetic mean, standard deviation, minimum, median, and maximum) of both raw and change from baseline data will be also presented. • CTCAE criteria (version 5) will be used to categorise laboratory safety data.

 • Statistical Analysis (Modelled) 	
 • No statistical modelling is planned.

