10.2. Appendix 2: Clinical Laboratory Tests

- The tests detailed in [Table 4](#) will be performed by the local laboratory.
- Protocol-specific requirements for inclusion or exclusion of participants are detailed in [Section 5](#) of the protocol.
- Additional tests may be performed at any time during the study as determined necessary by the investigator or required by local regulations.

Table 4 Protocol-Required Safety Laboratory Assessments

Laboratory Assessments	Parameters			
Haematology	Platelet Count	RBC Indices: MCV MCH MCHC		WBC count with Differential: Neutrophils Lymphocytes Monocytes Eosinophils Basophils
	RBC Count			
	Haemoglobin			
	Haematocrit Reticulocyte % Reticulocytes			
Clinical Chemistry ¹	Urea	Potassium	Aspartate Aminotransferase (AST)/ Serum Glutamic-Oxaloacetic Transaminase (SGOT)	Total and direct bilirubin
	Creatinine	Sodium	Alanine Aminotransferase (ALT)/ Serum Glutamic-Pyruvic Transaminase (SGPT)	Total Protein Albumin
	Glucose ³	Calcium	Alkaline phosphatase	Lipids (fasted) ² : Total Cholesterol HDL LDL Triglycerides
	INR ⁴	APTT ⁴		
Routine Urinalysis	
 • Specific gravity • pH, glucose, protein, blood, ketones, by dipstick • Microscopic examination (if blood or protein is abnormal) 			

Laboratory Assessments	Parameters
Other Screening Tests	
 • Breath alcohol and urine drug screen (to include at minimum: amphetamines, barbiturates, cocaine, opiates, cannabinoids and benzodiazepines)] • Serology [(HIV antibody, hepatitis B surface antigen [HBsAg], hepatitis B core antibody [HBcAb], and HCV antibody) • QuantiFERON test for TB

NOTES :

1. Details of liver chemistry stopping criteria and required actions and follow-up assessments after liver stopping or monitoring event are given in Section 7 and [Appendix 7](#) All events of ALT $\geq 3 \times$ upper limit of normal (ULN) and bilirubin $\geq 2 \times$ ULN (>35% direct bilirubin) or ALT $\geq 3 \times$ ULN and international normalized ratio (INR) >1.5, if INR measured, which may indicate severe liver injury (possible Hy's Law), must be reported as an SAE (excluding studies of hepatic impairment or cirrhosis).
2. Blood for lipids (fasted) will be taken at pre-dose on day 1 and at day 21
3. Non-fasting sample except for pre-dose on day 1 and day 21.
4. Blood for INR and APTT will be taken at screening.

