2.2. Study Objective(s) and Endpoint(s)

Objectives	Endpoints
Primary Objectives	Primary Endpoints

 To evaluate the safety and tolerability of a single SC dose of GSK2330811 in healthy Japanese participants 	
 Number of participants reporting AEs. Number of participants reporting SAEs. Number of participants with vital signs (blood pressure, heart rate, body temperature) reaching a threshold of potential clinical importance Number of participants with treatment emergent abnormal ECG findings. Number of participants with CTCAE grade 1 or higher safety laboratory results (clinical chemistry, haematology values where CTCAE grading applies). Number of participants with treatment emergent abnormal urinalysis findings
Secondary Objectives	Secondary Endpoints

 To evaluate the pharmacokinetic (PK) profile of a single SC dose of GSK2330811 in healthy Japanese participants To assess the potential for anti-drug antibody formation following a single SC dose of GSK2330811 in healthy Japanese participants To assess effects of GSK2330811 on platelets and haemoglobin in healthy Japanese participants 	
 Pharmacokinetic parameters (Cmax, AUC, CL/F, Tmax, t_{1/2}, V_{ss}/F) Number of participants with anti-GSK2330811 antibodies Platelet nadir Time to platelet nadir Haemoglobin nadir Time to haemoglobin nadir
Exploratory Objectives	Exploratory Endpoints

 To explore the PD and the PK/PD relationship for GSK2330811 in the blood of healthy Japanese participants 	
 Serum levels of free OSM Serum levels of total OSM Levels of Thrombopoietin (TPO) Levels of Erythropoietin (EPO)

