3.16.	Safety	SAFE_T4	Summary of Worst Case Urinalysis Results Post-Baseline Relative to Baseline	Tests to include: Urine blood, Urine Glucose (dipstick), Urine Ketones (dipstick), Urine Microscopy – Bacteria, Urine Microscopy - Red Blood Cells, Urine Microscopy - White Blood Cells, Urine Protein (dipstick), Urine Specific Gravity	SAC
ECG					
3.17.	Safety	EG1	Summary of ECG Findings		SAC
3.18.	Safety	EG2	Summary of ECG Values	Footnote: Average used for triplicate ECG measurements	SAC
3.19.	Safety	EG2	Summary of Change from Baseline in ECG Values	Footnote: Average used for triplicate ECG measurements	SAC
Vital Signs					
3.20.	Safety	VS1	Summary of Change from Baseline in Vital Signs		SAC
3.21.	Safety	VS7	Summary of Worst Case Vital Signs Results Relative to Potential Clinical Importance (PCI) Criteria Post-Baseline Relative to Baseline		SAC

CONFIDENTIAL

208564

Safety: Tables					
No.	Population	IDSL / Example Shell	Title	Programming Notes	Deliverable [Priority]
3.22.	Safety	SAFE_T5	Summary of Worst Case Vital Sign Results Relative to Change from Baseline Potential Clinical Importance (PCI) Criteria		SAC
Immunogenicity					
3.23.	Safety	IMM1	Occurrence of Anti-Drug Antibodies	Add footnote: Note: The denominator for confirmed positive is the total number of subjects at that visit who have immunogenicity data available.	SAC

CONFIDENTIAL

208564

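### Table 3.16, the only summary table for the urinalysis primary endpoint, cannot report it: falls to Low specific gravity are pooled with no change, pH is left out, and no row counts participants across tests.

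*SAP*

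**What the plan says.** The SAP (section 2.2) and the protocol (section 3) list as a primary endpoint: "Number of participants with treatment emergent abnormal urinalysis findings". Protocol 9.4.2 sets the analysis for endpoints of this type: "For count data, the number and percentage of participants will be presented".

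SAP 12.9.5 has one urinalysis table, 3.16: "Summary of Worst Case Urinalysis Results Post-Baseline Relative to Baseline". Its list of tests covers blood, glucose, ketones and three microscopy items, and ends with "Urine Protein (dipstick), Urine Specific Gravity". pH is not on the list, although Protocol 10.2 (Appendix 2) collects "pH, glucose, protein, blood, ketones, by dipstick".

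The shell in SAP 12.10 assigns each test a floor value. For specific gravity this is "SG_URG (minimum value=Low". The rows for that test are *No Change/Decreased*, *Any Increase*, "Increase to NORMAL" and *Increase to HIGH*. The other urinalysis output is Listing 23, which is at subject level.

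**The concern.** The endpoint is a count of people. The table is a set of separate per-test blocks, each built around upward movement from a floor. That works where the floor is the normal result, as with dipstick blood, protein, glucose and ketones. It does not work for specific gravity, where the floor is an out-of-range category and Normal lies in the middle.

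Nothing else in the SAP fills the gap. Section 7.2 refers to sponsor standards and to Appendix 9. Appendix 7 sets criteria for haematology, chemistry, ECG and vital signs but none for urinalysis. The shell is therefore the only place in the SAP that says how the endpoint would be tabulated. If it is programmed as written, the report has no table giving the number and percentage the protocol asks for.

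**Working it through.** The documents give no figure to reproduce, so the check is a classification exercise followed by a short count.

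**Step 1. Specific gravity, one post-dose result.** The inputs are the ranking Low < Normal < High and the four rows in SAFE_T4. An upward step goes to *Any Increase*; everything else goes to *No Change/Decreased*. The SAP does not define an abnormal urinalysis finding, so two assumed definitions are compared:

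- A: the post-dose category is outside Normal and differs from baseline.
- B: any post-dose category outside Normal, which is how the timing-only rule in SAP 12.3.1 would read.

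| Baseline → post-dose | Row in the shell | Abnormal under A | Abnormal under B |
|---|---|---|---|
| Low → Low | No Change/Decreased | no | yes (mismatch) |
| Low → Normal | Any Increase | no (mismatch) | no (mismatch) |
| Low → High | Any Increase | yes | yes |
| Normal → Low | No Change/Decreased | yes (mismatch) | yes (mismatch) |
| Normal → Normal | No Change/Decreased | no | no |
| Normal → High | Any Increase | yes | yes |
| High → Low | No Change/Decreased | yes (mismatch) | yes (mismatch) |
| High → Normal | No Change/Decreased | no | no |
| High → High | No Change/Decreased | no | yes (mismatch) |

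Under A, 3 of 9 changes are mismatched. Under B, 5 of 9 are; the two extra are unchanged abnormal values, which any table of change from baseline would leave out. Three mismatches appear under both definitions: Low → Normal, Normal → Low and High → Low. The first can be subtracted because it has its own row. The other two cannot be separated from true no-change.

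**Step 2. Several post-dose results.** SAP 12.2.1 has urinalysis windows at Days 7, 21, 84 and 126. If worst case means the highest category in the ranking:

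- Baseline Normal with later Low and Normal results has worst value Normal and shows no change.
- Baseline High with later Low and High results has worst value High and shows no change.

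**Step 3. Safeguards.** The shell's programming note asks for an alert when a character value is neither the minimum nor shown as an increase. Low is the minimum, so a new Low never triggers it. SAP 12.5.1 says a participant with both High and Low post-baseline values counts in both categories, but SAFE_T4 has no Low category to count in.

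**Step 4. Participant count.** Suppose, for illustration only, that blood and protein each show an increase in 2 of 7 active participants. The number with either finding lies between max(2, 2) = 2 and min(7, 2 + 2) = 4, that is 2/7 = 29% to 4/7 = 57%. The table cannot say which. This gap would remain if specific gravity were removed.

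**The case against.** The strongest reply is that the data are not lost. Listing 23 covers every enrolled participant, about 10 and at most 14, and the count can be made from it by hand. Urinalysis results judged clinically significant are also recorded as adverse events (Protocol 10.3.1). The study is descriptive, with no hypothesis test, and no study stopping criterion names urinalysis. Whether a low specific gravity or an out-of-range pH matters clinically is a judgement the documents do not make.

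Most of this stands and limits the consequence. It does not supply the planned summary. SAP 12.4.2 keeps subject-level listings out of the main report body, and a hand count would need a definition of abnormal that the SAP does not give.

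Three stronger readings are tempting and are not supported:

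- **That the table treats a return to normal as harm.** The shell labels no increase as an event or as harm, and "Increase to NORMAL" is a visible, separate row.
- **That missing baseline microscopy loses participants.** Protocol 10.2 specifies "Microscopic examination (if blood or protein is abnormal". Where blood and protein were normal at baseline, later microscopy is triggered by a new dipstick abnormality that the dipstick rows already count. Where either was abnormal at baseline, baseline microscopy should exist.
- **That a specific gravity error shifts the reported endpoint rate by a known amount.** The documents give no frequency of such changes, and the table has no endpoint rate to shift.

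The figures in the shell are template placeholders, so rows that do not add up are not errors.

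**Conclusion.** The point holds as a defect in a planned display. Table 3.16 is the only summary table for this primary endpoint, and as specified it cannot give the participant count, for three separate reasons: new Low specific gravity is not identifiable, pH is absent, and there is no row across tests.

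The size can be stated only as a classification result: 3 of 9 specific gravity changes under definition A, 5 of 9 under definition B, with the two changes to Low unrecoverable under both. How many participants would be affected is unknown. The result assumes that out-of-range specific gravity in either direction counts as abnormal and, for repeated results, that worst case means the highest category. If the sponsor regards low specific gravity as unimportant, the SAP should say so; the missing participant-level row would remain. The sponsor's core display standards are not reproduced in the SAP and were not available to check.

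**What to change.** Change shell SAFE_T4 and the notes for Table 3.16 before final unblinding:

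1. For specific gravity, replace the rows with To Low, To Normal or No Change, and To High, relative to baseline. Count a participant with both Low and High in both, in line with SAP 12.5.1.
2. Add pH with the same rows, judged against the laboratory reference range.
3. Keep the existing increase rows for the dipstick and microscopy tests, so that worsening from an abnormal baseline (protein 1+ to 3+, for example) is still shown.
4. Add one row with the number and percentage of participants who have any post-dose urinalysis result that is outside normal and new or worse than baseline. State what counts as outside normal for each test.
5. Reconcile that definition with SAP 12.3.1, which classifies assessments as treatment emergent by timing alone.

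The cost is shell and programming changes only; no new data are needed.
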